#### Secondary analyses

To assess the prognostic impact of CAPA, 90-day survival in patients with and without CAPA after 1:1 matching was presented graphically using Kaplan-Meier curves, and compared with the log-rank test. To partly avoid immortal time bias, Kaplan-Meier curves were built as landmark analyses with different time of origin (15, 30, and 45 days after ICU admission) including patients still on follow-up at the selected time of origin, and excluding patients developing CAPA after the selected time of origin. It should be acknowledged that residual immortal time bias was present in patients from Genoa and Rennes in this secondary analysis, owing to their matching for time at risk (for the development of CAPA) in the primary study analysis (i.e., patients from Genoa and Rennes always remained alive for at least the time at risk of their respective case from Graz in the primary analysis). A sensitivity survival analysis was also conducted after 1:1:1 matching.

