### Matching procedure

#### *1:1 matching*

Each patient from Graz (i.e., undergoing posaconazole prophylaxis) was matched as a case with one control from Genoa and one control from Rennes (i.e., not undergoing posaconazole prophylaxis), employing two separate 1:1 propensity score (PS) matching procedures (one for identifying the control from Genoa and one for identifying the control from Rennes) [2,3]. The following variables were considered for matching cases with controls: (i) age; (ii) sex; (iii) treatment with tocilizumab; (iv) time at risk. We did not match for systemic steroid treatment since all patients from Graz received systemic steroids, thus we consider for possible match only those controls receiving systemic steroids in Genoa and Rennes (i.e., the majority of patients in the two centers). Time at risk was defined as follows: (i) for cases: days on posaconazole prophylaxis plus, if present, days in intensive care unit before posaconazole prophylaxis initiation; (ii) for controls: days in intensive care unit. In order to guarantee equal time at risk in cases and respective controls, we started by matching the case with the longest time at risk (53 days) to possible controls with time at risk equal or longer than 53 days. Then, we selected the case with the second longest time at risk and possible remaining controls with equal or longer time at risk. The procedure was repeated until all cases were matched to one control from Genoa and one control from Rennes. Eventually, for the study analyses, we considered only the period of time at risk in controls (starting from intensive care unit admission) that was equal to the time at risk in the respective case (in order to have an exactly equal time at risk in cases and their respective controls).

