**Table 1. Demographic and clinical characteristics of patients before matching**

Variables*	Graz (n = 83)	Rennes (n = 192)	Genoa (n = 239)	P	SD (Graz vs. Rennes)	SD (Graz vs. Genoa)	SD (cases vs. controls)
Posaconazole prophylaxis	83 (100)	0 (0)	0 (0)	<0.001	Inf.	Inf.	Inf.
Age at ICU admission in years, median (IQR)	65 (58-71)	64 (55-71)	64 (56-71)	0.640	0.122	0.072	0.095
Male sex	56 (68)	125 (65)	178 (75)	0.095	0.064	-0.156	-0.043
Treatment with tocilizumab	2 (2)	6 (3)	56 (23)	<0.001	-0.064	-0.670	-0.454
Systemic steroid treatment	83 (100)	169 (88)	187 (78)	<0.001	0.522	0.751	0.640
Length of ICU stay in days, median (IQR)	18 (13-33)	14 (10-27)	21 (12-42)	<0.001	0.256	-0.164	-0.008

ICU, intensive care unit; IQR, interquartile range; SD, standardized difference in means or proportions divided by standard error; imbalance defined as absolute value greater than 0.20 (small effect size)

\* Expressed as n (%), unless otherwise indicated

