**Table 2. Incidence rate and incidence rate ratio of CAPA before matching**

Center	IR	
Graz (posaconazole prophylaxis)	1.69 CAPA/1000 patient-days in ICU	
Rennes (no posaconazole prophylaxis)	4.50 CAPA/1000 patient-days in ICU	
Genoa (no posaconazole prophylaxis)	3.01 CAPA/1000 patient-days in ICU	
Center	IRR (95% CI)*	P*
No prophylaxis (Rennes and Genoa) vs. prophylaxis (Graz, reference)	2.38 (0.87-9.08)	0.0720

CAPA, coronavirus disease 2019 (COVID-19)-associated pulmonary aspergillosis; CI, confidence interval; ICU, intensive care unit; IR, incidence rate, IRR, incidence rate ratio. Calculation of IR were as follows:

$$IR_{Graz} = (4 \text{ CAPA}/2368 \text{ patient-days in ICU}) * 1000 = 1.69 \text{ CAPA}/1000 \text{ patient-days in ICU}$$

$$IR_{Rennes} = (38 \text{ CAPA}/8437 \text{ patient-days in ICU}) * 1000 = 4.50 \text{ CAPA}/1000 \text{ patient-days in ICU}$$

$$IR_{Genoa} = (12 \text{ CAPA}/3989 \text{ patient-days in ICU}) * 1000 = 3.01 \text{ CAPA}/1000 \text{ patient-days in ICU}$$

\* The exact Poisson method was employed for calculating 95% CI. The P-value is from exact mid-P test.

Overall, 4, 38, and 12 cases of CAPA were registered in Graz, Rennes, and Genoa, respectively. The distribution of proven, probable, and possible CAPA in the different centers was as follows: Graz (n = 0 proven, n = 3 probable, n = 1 possible); Rennes (n = 0 proven, n = 19 probable, n = 19 possible); Genoa (n = 0 proven, n = 12 probable, n = 0 possible).

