**Table 5. Multivariable logistic regression of factors associated with development of CAPA after 1:1 matching**

Variables	OR (95% CI)	P
EORTC/MSGERC risk factor present at ICU admission	4.35 (1.15-16.49)	0.031
ECMO	1.85 (0.34-9.99)	0.475
Center		0.007
Rennes (vs. Graz as reference)	6.07 (1.76-20.91)	0.004
Genoa (vs. Graz as reference)	0.59 (0.10-3.53)	0.566

CI, confidence interval; CAPA, coronavirus disease 2019 (COVID-19)-associated pulmonary aspergillosis; ECMO, extracorporeal membrane oxygenation; EORTC, European Organization for Research and Treatment of Cancer; ICU, intensive care unit; IQR, interquartile range; MSGERC, Mycoses Study Group Education and Research Consortium; OR, odds ratio.

Overall, 4, 17, and 2 cases of CAPA were registered in Graz, Rennes, and Genoa, respectively, after 1:1 matching. The distribution of proven, probable, and possible CAPA in the different centers was as follows: Graz (n = 0 proven, n = 3 probable, n = 1 possible); Rennes (n = 0 proven, n = 10 probable, n = 7 possible); Genoa (n = 0 proven, n = 2 probable, n = 0 possible).

[figure not shown]
**Table 6 (sensitivity analysis). Multivariable logistic regression of factors associated with development of CAPA after 1:1:1 matching**

Variables	OR (95% CI)	P
EORTC/MSGERC risk factor present at ICU admission	2.84 (0.70-11.63)	0.146
ECMO	1.48 (0.29-7.50)	0.639
Center		0.002
Rennes (vs. Graz as reference)	5.10 (1.54-16.90)	0.008
Genoa (vs. Graz as reference)	0.80 (0.17-3.80)	0.776

CI, confidence interval; CAPA, coronavirus disease 2019 (COVID-19)-associated pulmonary aspergillosis; ECMO, extracorporeal membrane oxygenation; EORTC, European Organization for Research and Treatment of Cancer; ICU, intensive care unit; IQR, interquartile range; MSGERC, Mycoses Study Group Education and Research Consortium; OR, odds ratio.

[figure not shown]
Overall, 4, 16, and 3 cases of CAPA were registered in Graz, Rennes, and Genoa, respectively, after 1:1:1 matching. The distribution of proven, probable, and possible CAPA in the different centers was as follows: Graz (n = 0 proven, n = 3 probable, n = 1 possible); Rennes (n = 0 proven, n = 9 probable, n = 7 possible); Genoa (n = 0 proven, n = 3 probable, n = 0 possible).

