**Figure 1. Flow-chart of the patient selection process**

[figure not shown]
**Figure 1 legend.** Matched cohorts after 1:1 and 1:1:1 matching were both composed of 249 patients, although some different controls could have been selected (for details, see matching methods). COVID-19, coronavirus disease 2019.

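### The effect of CAPA on survival is assessed only in cohorts matched for the posaconazole question, which leaves an avoidable and untested immortal-time bias, CAPA unbalanced against no CAPA, and as few as 23 of 54 CAPA cases

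*SAP*

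**What the plan says.** The SAP section Secondary analyses sets out to assess the prognostic impact of CAPA and reports that "90-day survival in patients with and without CAPA after 1:1 matching was presented graphically using Kaplan-Meier curves", compared by the log-rank test. Curves start at days 15, 30 and 45 after ICU admission. They include patients still followed at that day and leave out those whose CAPA came later. The section concedes that immortal-time bias remains for Genoa and Rennes, "owing to their matching for time at risk (for the development of CAPA) in the primary study analysis". The only sensitivity analysis repeats the curves after 1:1:1 matching. No survival analysis of unmatched patients is described.

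The cohort is defined in the section on 1:1 matching. Each Graz patient (all on posaconazole) receives one Genoa and one Rennes control, matched on age, sex, tocilizumab and time at risk. Only steroid-treated controls are eligible, and a control must have at least as many ICU days as the case has days at risk. The section ends by saying that "for the study analyses, we considered only the period of time at risk in controls" that equals the case's time at risk.

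The counts are in the table notes. Before matching: "Overall, 4, 38, and 12 cases of CAPA were registered in Graz, Rennes, and Genoa, respectively" (Table 2). Then: "Overall, 4, 17, and 2 cases of CAPA were registered in Graz, Rennes, and Genoa, respectively, after 1:1 matching" (Table 5), and "Overall, 4, 16, and 3 cases of CAPA were registered in Graz, Rennes, and Genoa, respectively, after 1:1:1 matching" (Table 6). The Figure 1 legend adds: "Matched cohorts after 1:1 and 1:1:1 matching were both composed of 249 patients".

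**The concern.** The exposure in this analysis is CAPA, but the cohort was built to compare posaconazole with no posaconazole. This has four consequences.

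- The matching gives no balance between patients with and without CAPA, and a log-rank test adds no adjustment.
- The requirement that controls stay in the ICU at least as long as their case is what creates the guaranteed survival time. The question about CAPA and survival does not need that requirement.
- The sensitivity analysis keeps the requirement, so agreement between the two sets of curves says nothing about the bias.
- Many CAPA cases in the control centres fall outside the matched set.

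A further point is unclear. The sentence limiting control time refers to the study analyses in general. If it governs the survival analysis too, CAPA status in a control is read only to the end of the window, which may be well before the landmark.

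At stake is how far the 90-day curves can be read as the effect of CAPA, rather than of centre and selection. The primary comparison of CAPA risk is not affected by this point.

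**Working it through.** **1. The plan's own figure.** The SAP states no sample size or power for the survival analysis. The nearest figure on the same 54 cases is the Table 2 rate ratio. (50/12426)/(4/2368) = 2.38, exact 95% CI 0.87 to 9.08, two-sided mid-P 0.0720. All three reproduce.

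**2. Cases and patients** (Tables 1, 2, 5 and 6; Figure 1 legend).
- Full cohort: 4 + 38 + 12 = 54 CAPA among 83 + 192 + 239 = 514 patients.
- 1:1 matched: 4 + 17 + 2 = 23 among 249. 1:1:1 matched: 4 + 16 + 3 = 23 among 249.
- Difference: 54 − 23 = 31, and 31/54 = 57%, all in the control centres (Rennes 38 to 17, Genoa 12 to 2, Graz 4 to 4).

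**3. Balance by centre in the 1:1 set.** Rennes gives 17/23 = 74% of CAPA patients and (83 − 17)/(249 − 23) = 66/226 = 29% of the others. Table 5 also associates an EORTC/MSGERC risk factor with CAPA (OR 4.35, 1.15 to 16.49), and the log-rank test ignores it.

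**4. Precision.** If the same fraction dies in both groups, the standard error of the log hazard ratio is proportional to √(1/n_CAPA + 1/n_other).
- Matched: √(1/23 + 1/226) = 0.219.
- Full: √(1/54 + 1/460) = 0.144.
- Ratio: 0.144/0.219 = 0.66, about one third smaller.

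The documents give no number of deaths. Assuming a hazard ratio of 2.0 and overall 90-day mortality of 30%, 40% or 50%, the Schoenfeld formula gives:

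| Assumed mortality | Power, 249 patients | Power, 514 patients |
|---|---|---|
| 30% | 41% | 75% |
| 40% | 52% | 86% |
| 50% | 61% | 93% |

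These figures ignore landmark exclusions, so they are upper bounds for landmark curves in either cohort.

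**5. Windows against landmarks.** Table 3 gives time at risk as median 15 days (IQR 10 to 23) for 83 patients per centre; the longest is 53 days.
- The median is the 42nd ordered value, so at least 42 windows end by day 15 and at most 41 run past it.
- The upper quartile lies between the 62nd and 63rd values, so at least 62 windows end by day 23. At most 83 − 62 = 21 can run past day 30 or day 45.

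Everyone in a landmark analysis is on follow-up at the landmark. Survival guaranteed before that day therefore gives no group an advantage. Only a control whose window outlasts the landmark has guaranteed survival after it: at most 41 per control centre at day 15, and at most 21 at days 30 and 45.

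**6. When CAPA status is read.** There are two possible readings.
- If the truncation applies, a control with CAPA between window end and landmark counts as CAPA-free. At least 62 of 83 control windows per centre end by day 23, so the gap exists for most triplets at days 30 and 45. The exclusion of later CAPA could then work only for windows longer than the landmark.
- If it does not apply, CAPA arising in matched controls after the window was counted. The curves may then hold more than 23 cases, and 31 is an upper bound on the loss.

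The Secondary analyses section does not say which.

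**The case against.** The SAP names the bias, its cause and the centres affected, and uses three landmarks to reduce it in an analysis that is only secondary. That is fair disclosure, and the landmarks do remove the part before each time of origin. But disclosure does not remove the rest, and the one sensitivity analysis cannot measure it.

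A reader might infer that all 166 controls, two thirds of the cohort, carry guaranteed survival into the curves. Step 5 shows otherwise. The guarantee also covers controls with and without CAPA, so the documents support no statement on which way the comparison is shifted.

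A reader might also infer that CAPA patients were in fact placed in the no-CAPA arm. The documents do not show this. The truncation sentence sits in the matching procedure, where it serves equal time at risk. Follow-up to 90 days and the exclusion of CAPA after day 15, 30 or 45 suggest that data beyond the window were used. What stands is an unstated ascertainment period.

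The loss of cases is roughly in proportion among controls: 31/50 = 62% of CAPA cases against 265/431 = 61% of patients. This tempers any claim of overall selective loss, although Genoa loses 10/12 = 83% of cases against 156/239 = 65% of patients. The loss of information remains.

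Finally, the full cohort is no better balanced by itself: Rennes gives 38/54 = 70% of CAPA patients and 154/460 = 33% of the others. That is correct, and it is why the replacement must be stratified and adjusted.

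**Conclusion.** The concern holds in limited form. The matched cohort does not suit a CAPA survival question: it leaves centre strongly associated with CAPA, carries a bias that the SAP itself traces to the matching, and is checked only against a cohort with the same condition. The bias beyond a landmark is confined to a minority of controls, fewer at the later landmarks, and has no derivable direction. The loss is up to 31 of 54 CAPA cases. The gain of about one third in standard error assumes equal death fractions and precedes landmark exclusions. Misclassification of CAPA status is conditional on the truncation rule reaching this analysis. The change should be made because the bias is avoidable, but the point concerns a secondary analysis only.

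**What to change.** In Secondary analyses, and in Figures 2 and 3:

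- Make the main analysis of CAPA and 90-day survival a model in all 514 patients, or all with known 90-day status, with CAPA as a time-dependent exposure from its diagnosis day. Alternatively, keep the three landmarks and read CAPA status up to each landmark, regardless of the matching window.
- Stratify by centre. Adjust for age, sex, systemic steroids and tocilizumab (2%, 3% and 23% in Graz, Rennes and Genoa, Table 1). Add EORTC/MSGERC risk factor and ECMO where recorded; Table 1 does not report these two before matching.
- Keep the 1:1 and 1:1:1 curves as sensitivity analyses, and state the period over which CAPA was ascertained for them.

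The cost is one re-analysis and revised wording. It assumes that 90-day vital status and CAPA dates are held for unmatched patients. The protocol's case report form lists outcome data but does not specify 90-day status, so this must be confirmed first. The change also brings in (192 − 169) + (239 − 187) = 75 patients without steroids (15% of 514), to be handled by the adjustment or by restriction to steroid-treated patients.

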**Figure 2. Landmark analysis of 90-day survival in patients with and without CAPA after 1:1 matching**

**Figure 2 legend.** Landmark survival analysis after 1:1 matching, with different time of origin (15, 30, and 45 days in ICU for panel A, B, and C, respectively). CAPA, coronavirus disease 2019 (COVID-19)-associated pulmonary aspergillosis; ICU, intensive care unit.

**Figure 3 (sensitivity analysis). Landmark analysis of 90-day survival in patients with and without CAPA after 1:1:1 matching**

**Figure 3 legend.** Landmark survival analysis after 1:1:1 matching, with different time of origin (15, 30, and 45 days in ICU for panel A, B, and C, respectively). CAPA, coronavirus disease 2019 (COVID-19)-associated pulmonary aspergillosis; ICU, intensive care unit.

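### The landmark survival curves drop patients who develop CAPA after the landmark, so the no-CAPA group is defined partly by future events (secondary analysis, small expected effect)

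*SAP*

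**What the plan says.** The SAP, Secondary analyses, compares 90-day survival between matched patients with and without CAPA by Kaplan-Meier curves and a log-rank test. It gives the reason for the landmark: "To partly avoid immortal time bias, Kaplan-Meier curves were built as landmark analyses with different time of origin". The landmarks are days 15, 30 and 45 after ICU admission. The rule for who enters the curves is "including patients still on follow-up at the selected time of origin, and excluding patients developing CAPA after the selected time of origin".

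The section then acknowledges residual immortal time bias in the Genoa and Rennes patients, "owing to their matching for time at risk (for the development of CAPA) in the primary study analysis". It says nothing about the effect of removing patients with later CAPA. The survival analysis in the 1:1:1 cohort is a sensitivity analysis to the matching. It uses the same three landmarks (Figure 3 legend) and describes no different rule.

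One related statement stands in the SAP section on 1:1 matching: "for the study analyses, we considered only the period of time at risk in controls (starting from intensive care unit admission", limited to the length of the matched case's time at risk. Survival, however, is followed to 90 days.

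**The concern.** A landmark removes immortal time bias because group membership is settled at the time origin and everyone then at risk is followed. Under the SAP's rule, membership of the no-CAPA group also depends on what happens after the origin. That brings back the kind of selection the landmark was meant to remove.

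The exclusion can move no-CAPA survival either way:

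- It removes patients who had to stay alive long enough to be diagnosed, which lowers the curve.
- It removes the deaths that follow a later CAPA diagnosis, which raises the curve.
- It removes patients who were still in ICU and so may have been at higher risk, which raises the curve.

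The net sign depends on the true effect of CAPA, on whether deaths occur in ICU or after discharge, and on when CAPA starts. If CAPA raises mortality, the exclusion tends to enlarge the apparent difference.

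At stake is the SAP's only described analysis of the prognostic impact of CAPA. The comparison of CAPA risk between centres is not affected.

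**Working it through.** **What the plan gives.** There is no survival estimate, event target or power statement for this analysis, and the figures are not in the text available. So there is no figure of the plan's own to reproduce, and the size has to be bracketed.

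**Inputs from the SAP.**

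- Matched cohort: 3 × 83 = 249 patients (Tables 3 and 4).
- CAPA after 1:1 matching: 4 + 17 + 2 = 23 (note to Table 5). After 1:1:1 matching: 4 + 16 + 3 = 23 (note to Table 6). Both are 23/249 = 9.2%.
- Time at risk: median 15 days, IQR 10-23 (Table 3), longest 53 days (1:1 matching).

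If CAPA counts only within matched time at risk, at most 23 patients can be affected. With an upper quartile of 23 days, few of them can have onset after day 30.

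**Identity.** Let k be the patients dropped for later CAPA, N the patients at the landmark and w = k/(N − early CAPA). Then

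shift in no-CAPA survival = w × (survival of never-CAPA − survival of later-CAPA).

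An extreme bound puts 22 of the 23 CAPA after the landmark, with a 30-point survival gap. The shift is 22/248 × 30 = 2.7 points if N = 249, and 22/124 × 30 = 5.3 points if N = 125.

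**Simulation with CAPA counted within matched time.** All hazards here are assumptions.

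- Time at risk was fitted to the median and IQR and capped at 53 days. The mean is 17.1 to 18.7 days, which gives 23/(249 × 18.7) = 4.9 to 23/(249 × 17.1) = 5.4 CAPA per 1000 days.
- CAPA probabilities by centre were 4/83, 17/83 and 2/83. Onset was uniform within time at risk or at constant hazard.
- Controls were alive in ICU to the end of time at risk. Graz patients left ICU at that point.
- Death hazard was 8, 12 or 18 per 1000 days, and after discharge either equal or one tenth. The 90 days ran from ICU admission.

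At day 15 the number dropped is 3.7-4.6 (uniform onset) or 5.5-7.3 (constant hazard), from a no-CAPA group of 201-221. It is up to 8 if onset simply follows the share of time at risk after day 15. At day 30 it is 0.4-2.2. The day-15 shift (excluding rule minus status fixed at the landmark) is:

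| CAPA death multiplier | Death hazard after discharge | Shift, points |
|---|---|---|
| 1 | equal | -0.34 to -0.07 |
| 1 | one tenth | +0.03 to +0.08 |
| 2 | equal | +0.30 to +0.53 |
| 2 | one tenth | +0.30 to +0.75 |

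At day 30 the shift is -0.09 to +0.38 overall.

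**Second simulation.** This one set 90-day mortality at 20, 35 or 50% and the hazard ratio of death after CAPA at 1, 1.5, 2 or 3. About 6 patients are dropped at day 15, 1.4 at day 30 and 0.2 at day 45. The day-15 shift is -0.2 to +0.9 points. At 35% mortality the day-15 hazard ratio with exclusion against status fixed at the landmark is 0.98 v 0.98 (true ratio 1), 1.94 v 1.91 (true ratio 2) and 2.87 v 2.78 (true ratio 3). Log-rank rejection at day 15 is 5.4% v 5.6% under no effect and 45.5% v 44.0% at a ratio of 2.

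**If CAPA counts over the whole ICU stay.** The rates used were 1.69, 3.65, 4.50 and 5.2 per 1000 ICU days. The second is the pooled Table 2 rate, (4 + 38 + 12)/(2368 + 8437 + 3989) = 54/14794. At a death hazard of 12 per 1000 days, 5.8, 11.6, 13.8 and 15.6 patients are dropped at day 15. Across all assumptions the day-15 shift is -1.3 to +2.1 points.

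**Scale.** In the first simulation about 14 to 18 CAPA patients remain at day 15. At an assumed 40% survival the standard error is √(0.24/18) = 11.5 to √(0.24/14) = 13.1 points.

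**The case against.** The exclusion is stated openly, and the SAP claims only to avoid immortal time bias in part. The shift is a small fraction of the standard error, its sign is not fixed, and days 30 and 45 are almost untouched. That all stands and is why the point is minor. Stating the rule is still not the same as stating its consequence.

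A sharper objection is that fixing status at the landmark is not clearly closer to the truth. With a built-in hazard ratio of 2, the SAP's rule gives 1.94 and the standard rule 1.91. The dilution is real. But the built-in ratio describes a time-dependent effect of CAPA. A landmark curve answers a different question, the outlook given status on that day, and for that question patients with later CAPA belong in the no-CAPA group.

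A third objection is that the first simulation has Graz patients leave ICU at the end of their time at risk. The SAP defines that time by days on posaconazole plus earlier ICU days. Graz ICU stay is longer: median 18 days (Table 1) and mean 2368/83 = 28.5 (Table 2). A further simulation that lets them stay on gives about 6 dropped at day 15 and about 1 at day 30. The day-15 shifts are -0.2 to +0.5 points for matched time and -0.8 to +1.3 for the whole stay, inside the ranges above. It remains true that every size rests on assumed hazards, so the decimals should not be over-read.

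Finally, the figures may already show numbers at risk. Their absence from the text is not held against the plan.

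**Conclusion.** The concern holds as a minor point. The no-CAPA group in the landmark curves is selected on events after the time origin, the SAP does not acknowledge the consequence, and no described sensitivity analysis removes it.

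The expected effect is about one survival point or less at day 15 if CAPA counts only within matched time at risk, and smaller at later landmarks. The wider range for the whole ICU stay arises mainly because the SAP does not say which CAPA events count. These sizes rest on assumed death hazards, discharge patterns and onset times. The structural point does not.

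Only a secondary, unadjusted comparison is concerned. The effect of posaconazole on CAPA risk is unaffected.

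**What to change.** - Replace the exclusion clause: set CAPA status at each landmark and keep patients who develop CAPA later in the no-CAPA group.
- Rerun the curves and log-rank tests for both the 1:1 and the 1:1:1 cohort.
- At each landmark report the group sizes, if the figures do not already show them, and the number with later CAPA.
- State whether CAPA after a control's matched time at risk counts in the survival analysis.

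The cost is one clause, one clarifying sentence and a rerun on existing data. The downside is some dilution of the contrast, which the reported counts of later CAPA make visible.

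Optionally, if CAPA dates and 90-day follow-up exist for all 83 + 192 + 239 = 514 patients, add a Cox model with CAPA as a time-dependent covariate, stratified by centre. That would address the matching bias the SAP already discloses: controls make up 19/23 = 83% of CAPA patients and 147/226 = 65% of the others. It is extra work, and the documents do not show whether it is feasible.
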